#### **Assessments and Evaluations:**

**Figure 2: Multiple Dose Study**

Day of Study	Scr	-3	1	3	7	10	14	17	21
Randomization			•						
Vital Signs/Body Weight	•	•	•	•	•	•	•	•	•
Complete Blood Chemistry	•				•		•		•
Physical Exam/EKG	•				•		•		•
OGTT		•			•		•		•
Plasma Metabolites					•		•		•
Insulin Secretory Assessment	•				•		•		•
Fasting Insulin/Glucose	•				•		•		•
Bioactives: Plasma/Excretion*					•		•		•
DXA		•							•
Adverse Event Assessment	•	•	•	•	•	•	•	•	•

**Figure 2: Proposed Study Design Assessing Multiple Dose Study for each Period.** There will be three study periods of assessment (see Table 2). SCR; Screening (only done in the first study period). A one day +/- visit window is allowed.

*\*NOTE Subjects will be given their intervention (low or high dose 5011-Nutrasorb or placebo) two hours prior to start of OGTT (0 hour) and will have plasma obtained at 0, 30 minutes, 1, 1.5, 2, 3, and 4 hours post ingestion. After initial void, urine will be collected over the 6 hour interval. These specimens will be measured in the Botanical Core lab. Note: Intervention will not be administered at Day -3 of each test period.*

**Baseline/Screening Evaluation:** All subjects will undergo an outpatient screening evaluation to assess their eligibility prior to entrance into the study. A complete medical history and physical examination will be performed. Blood samples will be taken for a complete blood chemistry, blood counts, thyroid hormone panel and urinalysis. Subjects with impaired glucose tolerance or diabetes will be excluded. During baseline, subjects will be assessed for dietary intake data and instructed on weight maintenance diets. A taste (small sip) of the study product will also be administered during screening.

**Randomization:** After completing initial physiological sequence, each subject will be assigned to a treatment sequence as follows: Nine subjects will be enrolled for each of the 3 cohorts to investigate 3 doses of extract as compared to placebo (Low Dose, Medium Dose and High Dose). These 9 subjects will be enrolled in 3 strata by body weight (BMI 18.5-24.9 kg/m^2, BMI 25-29.9 kg/m^2, and BMI 30-40 kg/m^2). Further, in each cohort, there are 3 possible orders (treatment sequences) in which the extract doses can be administered. In each cohort, it is desirable to have 1 participant from each BMI stratum in each treatment sequence. In each cohort, the first 3 participants enrolled in each BMI stratum will be randomly assigned to one of the 3 treatment sequences for that cohort. The statistician, [name], will use SAS V9.3 to prepare 3 randomization schedules (one for each BMI stratum) for the pharmacist. Each list will have 3 blocks of the 3 randomly permuted treatment sequences. The pharmacist will determine the BMI stratum for each enrollee in turn and dispense the treatments according to the next

available treatment sequence assignment on the randomization schedule for that participant's BMI stratum. [name] and the Pennington pharmacist have a long history of collaboration in this type of trial.

The dose to be used in the multiple dose study will be based on our dose ranging Phase I study. As outlined in Section 2B, based on the data collected in the SAD study which will consist of plasma appearance of bioactives, safety and tolerability, and biological response, the dosing for the MAD will be determined. As also stated, consideration will be given to providing the extract in BID or TID dosing if data suggests that approach. The 5011-Nutrasorb used in human studies will be standardized using QA/QC concentration parameters established by the Botanical Core. The randomization will be blinded to the staff performing the physical measures, metabolic testing, performance of assays, entering or calculating data related to the study and study investigators to assure minimal potential sources of bias.

*Nutrition Assessment:* Subjects' usual dietary intake will be assessed by a research dietitian at screening and monitored throughout the study. The dietary intake analysis will be valuable as a method of evaluating consistency in dietary regimen over the study period. Biochemical profiles will be monitored to assess safety and body weights will be obtained at each study visit.

## **4. SELECTION AND ENROLLMENT OF PARTICIPANTS**

### **4.1 Inclusion Criteria**

Participants must meet all of the inclusion criteria to participate in this study.

#### **SINGLE AND MULTIPLE DOSE COHORT**

For **the single and multiple dose studies** to assess safety and tolerability, we will evaluate **healthy subjects**. Deviations from inclusion criteria for these studies are not allowed because they can potentially jeopardize the scientific integrity of the study or subject safety. Therefore, adherence to the criteria as specified in the protocol is essential.

A subject will be deemed as "healthy" and eligible for inclusion in this study only if all of the following criteria apply:

- Healthy as assessed on a medical evaluation including medical history, physical examination, laboratory tests and cardiac monitoring.
- Males and females between 18 and 65 years of age inclusive at the time of signing the informed consent.
- Women of child-bearing potential must agree to use one of the approved contraception method [(i.e., barrier method, intrauterine and cervical devices, oral contraceptives, hormonal injections (Depo Provera®), condoms with spermicidal gel or foam, contraceptive patch (Ortho Evra), diaphragm, or abstinence)], prior to the start of dosing to sufficiently minimize the risk of pregnancy at that point. Female subjects must agree to use contraception until the follow-up visit.

- BMI within the range 18.5 – 32 kg/m^2 (rounding up or down as appropriate is permitted for calculation), for both males and females for the single dose studies, and a BMI of 18.5 – 40 kg/m^2 for the multiple dose study.
- Capable of giving written informed consent, which includes compliance with the requirements and restrictions listed in the consent form.

## 4.2 Exclusion Criteria

### **SINGLE AND MULTIPLE DOSE COHORT**

A subject will not be eligible for inclusion in this study if any of the following criteria apply:

- Subjects with a prior history of Type 2 diabetes.
- Women who are pregnant or who are lactating.
- Women of childbearing potential who are not using an effective method of birth control(i.e., barrier method, intrauterine and cervical devices, oral contraceptives, hormonal injections (Depo Provera® ), condoms with spermicidal gel or foam, contraceptive patch (Ortho Evra), diaphragm, or abstinence), are not surgically sterilized (including tubal ligation and hysterectomy), or not at least 2 years postmenopausal. All women of childbearing potential will have a pregnancy test performed prior to starting the study treatment in each phase. If a subject becomes pregnant during the study, they will be dropped from the study.
- Subjects who have type 1 diabetes.
- Subjects who are on concomitant therapy with glucocorticoids (except topical or inhalant glucocorticoids). Other medications that have an effect on glucose homeostasis (i.e. ACE inhibitors) are acceptable if they have been administered in a stable dosage during the preceding 6 months and dosage will continue unchanged during the study.
- Subjects with a history or evidence of significant gastrointestinal dysfunction, e.g. irritable bowel syndrome; inflammatory bowel disease; ulcerative colitis or Crohn's disease; regional enteritis; diverticulosis or diverticulitis; significant gastroparesis; GI stricture, partial or complete gastrectomy or small bowel resection; autonomic neuropathy consisting of dysphasia; delayed gastric emptying or diarrhea; chronic, severe constipation; peptic ulceration, colonic ulceration, or GI bleeding.
- Subjects who are taking concomitant therapy with medications known to be nephrotoxic, such as aminoglycosides, methicillin, and cyclosporin.
- Subjects who have evidence of clinically significant renal dysfunction or disease, e.g. serum creatinine >1.5 mg/dL in males and >1.4 mg/dL in females and/or BUN >50 mg/dL, proteinuria of >1 gram/day or 4+ proteinuria on dipstick urinalysis.
- Subjects with clinically significant cardiovascular dysfunction and/or history (within the preceding 6 months) of significant cardiovascular dysfunction, e.g., congestive heart failure or serious arrhythmia, myocardial infarction, cardiac surgery; transient ischemic attacks or cerebrovascular accident during the preceding six months; diagnosis of symptomatic autonomic neuropathy with a history of orthostatic hypertension, syncope,

or hypertension with a systolic blood pressure of  $\geq 180$  mm Hg and diastolic blood pressure  $\geq 110$  mm Hg at the time of screening visit.

- Subjects with EKG findings deemed by the medical investigator as “clinically significant” will be excluded. These findings include: ST changes suggesting ischemia, myocarditis, infarction, bundle branch blocks, PVCs, ventricular arrhythmias, or ventricular paced beats from pacemaker.
- Subjects who have evidence within the preceding 6 months of hepatic disease or dysfunction, e.g. AST, ALT, alkaline phosphatase or total bilirubin twice the upper limit of normal; hepatitis; jaundice; cirrhosis.
- Subjects with clinically significant pulmonary, neurologic, hematologic, immunologic, neoplastic or metabolic disease.
- Subjects with evidence or recurrence of malignancy within the past five years, other than excised basal cell carcinoma.
- Subjects for whom surgery is anticipated during the study period.
- Subjects with a history of substance abuse or alcoholism within the past 5 years, or significant psychiatric disorder that would interfere with the subject's ability to complete the study.
- Subjects who have donated blood during the month prior to study entry or planned during the study.
- Subjects who have participated in other studies using an investigational drug during the preceding 3 months.
- Subjects who are current smokers or have smoked within the previous 6 months. No smoking will be allowed during the study.
- Subjects that have had a fluctuation in body weight  $>5\%$  in the preceding 2 months.
- Subjects who are taking prescription or over the counter medication or supplements for desired weight loss.
- Subjects who have an allergy to soy

#### **4.3 Study Enrollment Procedures**

- The goal is to enroll and complete all subjects in a 9 month period. This will require enrolling 9 subjects per month.
- Potential participants will be identified through the Pennington Biomedical Research Center's participant database (over 70,000 people are in the database). The database can be queried for specific inclusion and exclusion criteria after receiving approval from the Pennington Biomedical Research Center's privacy board. Pennington Biomedical has an exceptional track record for recruiting healthy individuals into early phase trials.
- Enrollment rates will be monitored by the study coordinator, investigator and recruiting department in order to ensure goals are met.
- Alternate methods of recruitment will be implemented as needed. Examples include community events, radio advertisements, television advertisements, newspaper articles and/or advertisements.

- Screening logs will be kept and all eligibility criteria reviewed by both the study coordinator and the investigator.
- Informed consent will be obtained according to Pennington Biomedical Research Center's Standard Operating Procedures.

### **Randomization procedure**

Each subject in the cohorts will be randomly assigned one of the relevant treatment sequences in order of enrollment. Treatment sequence assignments will be balanced so that each sequential block will have unique treatment sequences. This randomization will be done by the study statistician. As an example, for the multiple dose study, the first 3 enrolled subjects in each cohort will be randomly assigned to one of 3 distinct treatment sequences, as will enrollees 4-6 and 7-9. As a result, 3 of the 9 subjects in each cohort will be randomly assigned to each of the 3 treatment sequences.

## **5. STUDY INTERVENTIONS**

### **5.1 Interventions, Administration, and Duration**

The product for the clinical studies will be obtained from the Botanical Core Lab of the Rutgers Component of the Botanical Research Center. Working in collaboration with [name] at the Louisiana State University (LSU) Food Science department, the final product will be delivered to the Pennington Biomedical Research Center where the clinical study will be performed. Specifically, *Artemisia dracunculus* herb was grown from seed by ARC Greenhouses. This crop of *Artemisia dracunculus* was grown in the Florida location of ARC Greenhouses. Only insecticidal soap approved for food applications was used as a pesticide. The herb was harvested and shipped to Shiloh, NJ in a cold container (4 °C, together with perishable fresh cut flowers) and flash frozen upon arrival. The frozen herb will be shipped frozen (-20 °C, together with frozen food) to LSU for processing.

The following steps for clinical product use are outlined as follows:

#### **1. 5011-Nutrasorb preparation**

- a) Frozen *Artemisia dracunculus* is extracted in DI water 1:5 (w/v).
- b) The water is heated to near boiling for 2 hrs (slow roll) and cooled overnight. Solids are removed by filtration using MiraCloth.
- c) The *Artemisia* "tea" is mixed with soy protein isolate (SPI) at a ratio of 30g of SPI/1Liter of water.
- d) The pH of the mixture is adjusted to 3.5 as a slurry using HCl.
- e) The SPI is separated from the mixture by centrifugation (removing supernatant from NS) or using centrifugal filtration.
- f) The PMI-5011 Nutrasorb is lyophilized to dryness.
- g) The final product will be administered as a powder and will be mixed with water immediately before planned ingestion.

## 2. Scale-up Procedure

- a) Scale-up will be conducted in batch wise operations.
- b) Frozen *Artemisia dracunculus* tissue will be prepared in 20 kg batches. 20 kg of plant issue will be suspended in 100 kg of water in a steam jacketed kettle equipped with mechanical stirring. The suspension will be brought to 100oC for 2 hours and then transferred to another kettle, allowed to cool for several hours and filtered through multiple layers of cheesecloth followed by filtration through a double layer of miracloth. Then 3000g of soy protein will be stirred into the solution. Stirring will be continued for 30 minutes. The suspension will then be adjusted to pH 3.5 with 1M HCl and allowed to settle for one hour.
- c) The bulk of the liquid will be decanted from the surface and the protein rich material will be centrifuged and the precipitate spread in trays and freeze dried.
- d) The microbial count and heavy metal analysis of the substance used for the trial will be performed by a licensed outside laboratory (Medallion Labs - [www.medlabs.com/](http://www.medlabs.com/)).

## Dosing Considerations

For consideration of the initial doses to be used in humans, we are aware that there are two ways that have been used to scale doses from mice to man or vice versa. The first one is based on body surface area and the second is the Kleiber formula of mass to the 0.75 power. For this study, we will use the Kleiber formula as we have had experience with this equation in the past (<http://home.fuse.net/clymer/minor/allometry.html>).

For our animal studies, successful effects were seen with PMI-5011 when used at a dose of 1%. Essentially, based on our calculations, mice were consuming approx. 4 grams of food per day. Given that the mice weigh about 40 g, this dose is approximately 1g/kg.

Based on data from the Botanical Research Center Core lab, the extract generally contains about 0.2% DMC-2 which is used as the reference standard. Therefore, based on the consumption of food containing 1% extract, the mice will be getting a daily dose of DMC-2 of  $0.002 \times 1000\text{mg/kg} = 2 \text{ mg/kg}$ . We have done gavage studies at 500 mg/kg doses which translates to a dose of DMC-2 of 1mg/kg. The amount of DMC-2 in the 5011-Nutrasorb is 0.1-0.2%. Based on these calculations, we would estimate that current dosing for humans would be 10 grams. However, we would like to evaluate low, middle and high dose for safety, tolerability, adverse effects and tolerability, our suggested dosing would be 0.3, 1, 3, 10, 20, and 30 grams for the SAD studies. Dosing for the MAD studies will be based on results for the most effective dose and side effect profile from the SAD study. As outlined in other sections of the proposal, dosing for the MAD studies will be determined based on PK analysis in SAD study in addition to assessment of adverse events and biologic response. Based on these parameters, we will have comprehensive data to suggest dosing for the MAD studies and frequency of dosing as to once daily, twice daily or three times daily.

### 5.2 Handling of Study Interventions

The product for the clinical studies will be obtained from the Botanical Core Lab of the Rutgers Component of the Botanical Research Center. Working in collaboration with [name] at

the Louisiana State University Food Science department, the final product will be delivered to the Pennington Biomedical Research Center where the clinical study will be performed.

The placebo will be the soy protein that has not been co-dried with the *Artemisia dracunculus* tea and will be modified using common food handling procedures (such as toasting or adding food colorant) so that it will have a similar appearance to the test material.

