### Sample Size and Population

For the safety and tolerability studies, healthy subjects who have passed all screening evaluations and have given informed consent will be recruited. Approximately 27 subjects (3 cohorts of 9 subjects) will participate in the single dose studies. For the multiple dose studies, we plan to enroll an additional 27 participants (3 cohorts of 9 subjects). In the single dose studies, participants will be healthy adults with BMI 18.5 – 32 kg/m^2. In the multiple dose studies, participants will be stratified by body mass index (BMI) so that 1 normal weight (BMI < 25), 1 overweight (BMI 25-29) and 1 obese (BMI 30+) participant will be in each treatment sequence. Observers will be blinded to treatment sequence for each participant until the database has been locked.

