**Dosing:** Twenty Seven subjects (3 cohorts of 9 subjects with 3 subjects (1 normal weight, 1 overweight and 1 obese) randomly assigned to each of 3 treatment sequences) will participate in a three period crossover treatment regimen with each treatment period comprising once daily dosing for 21 days. Subjects will be randomly assigned to receive the treatments in the sequence orders shown in **Table 2**: 1) Cohort 1 will comprise 3 sequences of 3 treatments where placebo is dose 0 of 5011-Nutrasorb, D1 is a low dose (0.3 g) of 5011-Nutrasorb and D2 a medium dose (1 g) of 5011-Nutrasorb; 2) Cohort 2 will comprise 3 sequences of 3 treatments where D2 is a medium dose (1 g) of the 5011-Nutrasorb and D3 (30 g) a high dose of the 5011-Nutrasorb; and 3) Cohort 3 will comprise 3 sequences of 3 treatments where D1 is a low dose (0.3 g) of the 5011- Nutrasorb and D3 a high dose (30 g) of the 5011-Nutrasorb. Dosing for the MAD study was determined by data obtained in the SAD study as outlined above. Specifically, as outlined in Table 1, we will have data on PK studies, safety and tolerability, and biological response. In addition, based on information from the plasma appearance data and from assessment of biological response, consideration will be given to providing dosing on a BID or TID regimen. All doses used in this phase have been tested in the single-dose portion of the protocol. In the single dose protocol, there was no observed signal for toxicity, tolerability or other adverse events noted. The doses evaluated in the single dose study are spread among all 3 cohorts and no new dose is being introduced in this phase. Blinded analysis of the glucose tolerance will be on-going during the study and dose changes will be made if necessary. Additionally, as stated, if none of these doses show adequate glucose tolerance effects then an additional cohort may be added to investigate a twice daily or three times a day dose. In each treatment period a single dose of the 5011- Nutrasorb will be administered daily

from days 1 to 21. Complete biochemical and hematologic assessments to evaluate safety will be obtained in addition to clinical monitoring for adverse events.

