## 9. STATISTICAL CONSIDERATIONS

### 9.1 General Design Issues

The trials described in this protocol are the first stage of testing *Artemisia* sp. extract in humans. The studies will be conducted in (1) an ascending single dose evaluation of doses 0.3, 1, 3, 10, 20, and 30 g; and (2) a multiple oral dose evaluation of 3 doses chosen from the first evaluation and denoted doses 1, 2, and 3 as described in Section 3, Study Design. The single dose evaluation will be conducted by studying 6 doses (amounts) of extract and a placebo in a series of 3-treatment, 3-period crossover trials. The 3 treatments (placebo or one of two doses of extract) will be given at weekly intervals each in a single dose followed by a 7 day washout period. Each crossover trial will consist of 3 sequences of treatments across the weekly intervals [each sequence being a different order for receiving a triad of 2 doses of extract and a placebo (dose 1, dose 2, placebo; dose 3, dose 4, placebo; dose 5, dose 6, placebo)]. The placebo can be taken in period 1, period 2 or period 3 and the extract is taken in the other two periods where the lower dose of extract is always taken in a period that precedes that of the higher dose]. The primary objective is to assess the safety and tolerability of ascending amounts of the extract for each amount given in a single dose. If no adverse effects are observed with a given pair of extract doses, the dose escalates (e.g. dose 1, dose 2, placebo escalates to dose 3, dose 4, placebo which escalates to dose 5, dose 6, placebo) and a new cohort of subjects is studied in a new crossover trial with each escalation.

The multiple dose evaluation will be conducted similarly by studying 3 doses (amounts) of extract and a placebo in a series of 3-treatment, 3-period crossover trials. The 3 treatments (placebo or one of two doses of extract) will each be given once daily across a 21 day period followed by a 7 day washout period. Each crossover trial will consist of 3 sequences of treatment (each sequence being a different order for receiving 2 doses of extract and a placebo where the lower dose of extract always precedes the higher dose). The primary purpose is to further investigate safety, tolerability and bioavailability of once daily consumption of the extract over a 7 day period.

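### Does the unstated placebo portion size undermine blinding and the dose-placebo contrasts in the multiple-dose study?

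*Combined protocol and SAP*

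**What the plan says.** Section 5.2 says the placebo is soy protein that has not been dried together with the tarragon tea, and that it is altered by ordinary food-handling steps ("such as toasting or adding food colorant) so that it will have a similar appearance to the test material"). Section 5.1 says the product is a powder mixed with water just before it is taken. Neither section gives a placebo weight, a drink volume or a filler.

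Section 3.B sets the multiple-dose cohorts. In Cohort 2, "D2 is a medium dose (1 g) of the 5011-Nutrasorb and D3 (30 g) a high dose". In Cohort 3, "D1 is a low dose (0.3 g) of the 5011- Nutrasorb and D3 a high dose (30 g"). Cohort 1 takes 0.3 g and 1 g. Every participant also has a placebo period, described only as dose zero of the product. Section 9.1 orders the treatments so that each sequence holds two doses and "a placebo where the lower dose of extract always precedes the higher dose".

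On blinding, the Précis says "Observers will be blinded to treatment sequence for each participant until the database has been locked". Section 6.2.3 extends this to staff, assay and data personnel and investigators, calls blinding critical, and sets rules for breaking the blind of an individual subject. Participants are not named as blinded.

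Section 9.6 compares product with placebo in mixed models for crossover data, with Tukey-adjusted pairwise comparisons of doses and placebo.

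**The concern.** Toasting and colouring can make two powders look alike, but they do not hide a 30-fold or 100-fold difference in amount. If each dose is served as its bare weight, a single placebo portion in Cohorts 2 and 3 cannot resemble both active portions. Two things would then be at stake.

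The first is masking. A participant who sees portion size, and knows the cohort's doses and the order rule, could work out some treatments. Adverse events are collected by asking participants how they feel (Section 7.2), so a recognised portion might colour the answers.

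The second is interpretation. The secondary objective in Section 3.B is the effect on glucose tolerance. With unequal soy, a difference between 30 g of product and a small placebo could come from the tarragon or from the extra protein. If the placebo weight also differed between cohorts and all cohorts were analysed together, a contrast with matched weights could pick up part of that effect too.

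**Working it through.** **Inputs.** Three cohorts, three sequences per cohort and three participants per sequence (Section 9.2); sequence orders from Table 3; doses of 0.3, 1 and 30 g from Section 3.B. The documents give no standard deviation, effect size or power for this comparison. Results are therefore in units of the within-subject SD, or as shares of an unknown powder-mass effect *d* (30 g of powder rather than 1 g or less).

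**1. Size.** 3 × 3 × 3 = 27, which agrees with Section 9.2. Cohorts taking 30 g: 2 × 9 = 18 of 27. Gaps: 30 − 1 = 29.0 g (Cohort 2) and 30 − 0.3 = 29.7 g (Cohort 3), against 1 − 0.3 = 0.7 g in Cohort 1.

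**2. Which contrasts could match.** The three contrasts in a cohort are low versus placebo, high versus placebo, and high versus low. A placebo at the low weight leaves two unmatched. A placebo at the high weight also leaves two. A weight in between leaves three. This holds only if active doses are not made up to a common weight.

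**3. What portion size would reveal.** Write s for a small portion and L for a large one.

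| Sequence | Placebo at low weight | Placebo at high weight |
|---|---|---|
| low, placebo, high | ssL: 1 period identified | sLL: 1 |
| low, high, placebo | sLs: 3 | sLL: 1 |
| placebo, low, high | ssL: 1 | LsL: 3 |
| Total | 5 of 9 | 5 of 9 |

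A weight in between gives 9 of 9. With three participants per sequence and two cohorts: 5 × 3 × 2 = 30 of 54 participant-periods, or 9 × 3 × 2 = 54 of 54. If all portions in a cohort weighed the same, portion size would identify none.

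**4. What would enter the contrasts.** Least squares on 27 × 3 = 81 observations, with 27 participant, 2 period and 3 treatment parameters, leaves 81 − 32 = 49 df. The outcome is set to 1 for a 30 g portion and 0 otherwise.

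| Scenario | 30 g − placebo | 1 g − placebo | 0.3 g − placebo |
|---|---|---|---|
| Small placebo everywhere | 1.000 *d* | 0 | 0 |
| 30 g placebo in Cohorts 2 and 3, small in Cohort 1; common periods | 0.145 *d* | −0.600 *d* | −0.545 *d* |
| Same, with period effects by cohort | 0.111 *d* | −0.556 *d* | −0.556 *d* |

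If each cohort is analysed separately, the weight-matched contrast carries 0 of *d*.

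**5. What recoding would cost.** Standard errors in within-subject SD, if placebo became a separate level for each weight (30 g in Cohorts 2 and 3, small in Cohort 1):

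| Contrast | One placebo level (49 df) | Placebo split by weight (48 df) | Ratio |
|---|---|---|---|
| 30 g versus 30 g placebo | 0.344 | 0.353 | 1.03 |
| 1 g versus 30 g placebo | 0.316 | 0.383 | 1.21 |
| 0.3 g versus 30 g placebo | 0.344 | 0.423 | 1.23 |
| 1 g versus small placebo | 0.316 | 0.453 | 1.43 |
| 0.3 g versus small placebo | 0.344 | 0.453 | 1.32 |

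For comparison, 30 g versus placebo has a standard error of 0.365 from Cohorts 2 and 3 alone (31 df) and 0.516 from one cohort (14 df). The low-dose contrasts pay most.

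**The case for a change.** The best case for a change is that the omissions are real, the dose gaps are the protocol's own, and Section 6.2.3 itself calls blinding critical. Stating the placebo weight and who is masked would take a few sentences. The arithmetic above is sound on its conditions. It stands that the plan as written does not show that portions are alike, and that a reader cannot tell whether participants are masked.

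The rest depends on facts that the documents do not supply. They never say that portions are unequal. The similar-appearance step and the rules for breaking a subject's blind suggest that participant masking was intended. The title and consent pages, where a masking label might stand, were not available. The identification counts need visible portion sizes and a participant who knows both the doses and the order rule; no text says that participants are told these. The leakage shares need one model across cohorts, which Section 9.6 does not state, and Section 9.1 describes a series of separate crossover trials. They also need a placebo weight that changes between cohorts, which nothing describes. The size of *d* is unknown.

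Section 7.2 also cuts the other way: non-leading questions are there to limit bias. Glucose and insulin are laboratory measurements, and the staff who run the tests and assays are blinded.

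There is one loose end. Section 3.B says "Dosing for the MAD study was determined by data obtained in the SAD study as outlined above", while the randomization text of the same study says "The dose to be used in the multiple dose study will be based on our dose ranging Phase I study" and Section 5.1 says "Dosing for the MAD studies will be based on results for the most effective dose and side effect profile from the SAD study". These passages must be reconciled on whether the multiple-dose doses are already set. That is an editing matter and does not affect the reasoning here.

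**Conclusion.** The concern does not call for a change to the plan. What the documents show is missing detail on portion make-up and participant masking, not a demonstrated mismatch. Whoever weighs the placebo has to fix its weight, and the analyst can learn it before interpreting any contrast.

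The possible changes gain little. A common drink volume would not conceal a 30-fold or 100-fold difference in powder. Equalising weights with extra soy would alter what low-dose participants ingest and would not match taste. Separate placebo levels would protect against an effect of unknown size, at a cost of 21% and 23% in standard error for 1 g and 0.3 g against a 30 g placebo. That makes it a reasonable optional sensitivity analysis if weights turn out to differ, but not a better main analysis.

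The primary objective is safety and tolerability of the complex, of which soy is a part, and Section 9.2 disclaims any power for efficacy. If portions do prove unequal, the unmatched contrasts in the 18 participants of Cohorts 2 and 3 should be read as complex versus soy, which is a matter of reporting.

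This rests on the doses in Section 3.B, on active doses being given without make-up for the worst-case counts (30 or 54 of 54 periods), and on a pooled model for the leakage shares and the standard errors in the last table.
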